## **6.2 Safety Hypotheses**

There are no formal safety hypotheses in this study.

## **6.3 Statistical Methods for Safety Analyses**

The analysis set for safety analysis is the safety analysis set unless otherwise stated.

### **6.3.1 Extent of Exposure**

### **6.3.2 Adverse Events**

All AEs occurring from when a subject signs informed consent to when a subject exits the study will be accounted for in the reporting. Analysis and presentation of AEs occurring during the screening period will be separated from those occurring during the post-surgery period where a comparative evaluation of post-surgery AEs is intended. A post-surgery AE is an AE that occurs that was not present prior to the study procedure or any pre-existing event that worsens following the study procedure. The period for post-surgery AEs analysis starts from when surgery procedure has begun to end of study.

Descriptive summaries (eye counts, event counts, and percentages) by procedure group for specific AEs will be presented by primary SOC and PT in the Medical Dictionary for Regulatory Activities (MedDRA; version 19.1 or later). Eye counts refer to the number of eyes with the respective AE of interest. Event counts refer to the number of occurrences of the respective AE of interest, regardless of whether an eye already had this event.

The SOC's will be presented in alphabetical order. PTs will be ordered with each SOC in decreasing order according to the total column. An eye with multiple ocular AEs of the same preferred term is only counted once toward the total of this preferred term and once toward the total of the SOC. Post-surgery AEs will be summarized for all eyes in the safety analysis set for the following tables:

- Ocular AEs
- Ocular serious AEs (SAEs)
- Adverse device effects (ADEs)

- Serious ADEs (SADEs)

Listings describing details of AEs will be provided. These will include:

- Ocular AEs for all eyes in the safety analysis set
- Ocular AEs for all eyes not in the safety analysis set
- Non-ocular AEs for all enrolled subjects
- Deaths for all enrolled subjects

These listings will also include AEs that occur after signing the informed consent but prior to surgery. They will comprise all events occurring during this period in any subject who consented to participate in the study.

### **6.3.3 Device Deficiencies**

The number of all device deficiencies will be tabulated by procedure group. A listing of all device deficiencies as recorded on the Device Deficiency page of the Global Library Forms will also be provided.

### **6.3.4 Slit Lamp Examination**

A listing will be provided which presents all eyes with an abnormality in any slit-lamp parameter by visit. The listing will include the following variables: procedure group, investigator, subject, age, sex, race, ethnicity, visit, eye, parameter, baseline value and value at the visit. Other slit lamp examination findings will be listed along with their MedDRA dictionary primary SOC and PT codes.

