	
The secondary endpoints are:
 
 • The mean CDE expended in the eye during surgery. • The mean estimated aspiration fluid used during surgery. • The mean aspiration time spent during surgery. 
The null and alternative hypotheses are the same for all secondary analysis and can be presented as:
 
Ho: $\mu_c \leq \mu_s$
 
H_i: $\mu_c > \mu_s$
 
where μ_c denotes the mean value in the CRS group and μ_s denotes the mean value in the standard manual technique group for each of the respective secondary endpoints. The secondary hypotheses will only be tested if the primary objective is met and each of the null hypotheses will be tested using a one-sided paired t-test.
 
[REDACTED]

	
The safety outcomes will be summarized with appropriate summary statistics and also listed. The study will employ an adaptive design with potential sample size adjustment based on the proportion of discordance in the primary effectiveness outcome between the study eyes. An interim analysis to assess the need for sample size re-estimation will be performed when the first 200 subjects who are randomized, treated and completed their assessment for the primary effectiveness at Month 1.

Sample Size Justification	
Based on recent clinical experience, the rates of success for the primary endpoint are assumed to be 83% and 75% for the CRS and standard manual technique arms, respectively.
 
An estimate of the discordance in outcome between eyes is not known; however, based on the assumed rates of 83% and 75% for the primary endpoint, the rate of discordance must be between 8% and 33%. For an initial sample size calculation, the midpoint value of this range, 21%, is assumed. Based on these assumptions, 267 subjects, treated contralaterally, are required to provide 90% power to reject the null hypothesis. If the proportion of discordance is 33% and all other assumptions stay the same a sample of 433 subjects is needed to provide 90% power.
 
The two samples (267 and 433) are inflated to account for up to 10% subject drop-out in the full analysis set (FAS) so the subject range increases to 300 to 500.

---------------------------	---

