15.7 Safety Analysis

Adverse Events

All information obtained on AEs will be summarized for ocular and nonocular AEs separately.

The number and percentage of all ocular AEs, including for either eye, will be tabulated by treatment and preferred term. An eye with multiple ocular AEs of the same preferred term is only counted once toward the total of this preferred term. A listing of nonocular AEs will be provided.

Device Deficiencies

The number and percentage of all device deficiencies will be tabulated by treatment. A listing of all device deficiencies will also be provided.

Other Safety Assessments

All other safety assessments (IOP, slit-lamp examination and dilated fundus examination) will be summarized. Number and percentage will be presented for categorical variables and descriptive statistics for continuous variables.

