### 4.3 Demographics and other Baseline Characteristics

Characteristics by subject will be summarized overall, and characteristics by eye will be summarized by procedure group and overall.

Demographics and background characteristics for each subject:

- Age (in years, and year categories < 65 and ≥ 65)
- Gender (male / female / unknown / undifferentiated)
- Ethnicity (Hispanic or Latino / not Hispanic or Latino / not reported / unknown)
- Race (White / Black or African American / American Indian or Alaska Native / Asian / Native Hawaiian or Other Pacific Islander / other)

Ocular characteristics for each eye:

- Axial length (mm)
- Keratometry

Note: variables that have both baseline and post-baseline values will be summarized elsewhere in the SAP: Intraocular pressure (IOP), ██████████ ██████████ manifest refraction, slit lamp examination.

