### **6.3.6 Dilated Fundus Examination**

A listing will be provided which presents all eyes with abnormality in any fundus parameter by visit. The listing will include the following variables: procedure group, investigator, subject, age, sex, race, ethnicity, visit, eye, baseline value and value at the visit.

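### SAP 6.3.4 and 6.3.6 plan only listings of slit-lamp and fundus abnormalities, where protocol 15.7 promises summaries with number and percentage

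*SAP*

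**What the plan says.** Protocol 8.4.2 and SAP 6.1 list the same six safety endpoints, among them slit-lamp examination and dilated fundus examination.

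Protocol 15.7 commits to a summary of both: "All other safety assessments (IOP, slit-lamp examination and dilated fundus examination) will be summarized". It gives the form in the next sentence: "Number and percentage will be presented for categorical variables and descriptive statistics for continuous variables". The synopsis treats a listing as additional to a summary: "The safety outcomes will be summarized with appropriate summary statistics and also listed".

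SAP 4.3 explains why some variables are left out of the baseline tables: "variables that have both baseline and post-baseline values will be summarized elsewhere in the SAP". The visible items in that note are IOP and "manifest refraction, slit lamp examination". Some items are redacted, and dilated fundus is not among the visible ones.

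The SAP sections that should carry the summaries plan listings. For slit lamp, 6.3.4 says: "A listing will be provided which presents all eyes with an abnormality in any slit-lamp parameter by visit". It adds: "Other slit lamp examination findings will be listed along with their MedDRA dictionary primary SOC and PT codes". For fundus, 6.3.6 says: "A listing will be provided which presents all eyes with abnormality in any fundus parameter by visit". Both listings include procedure group, visit, eye, baseline value and value at the visit.

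**The concern.** A listing of abnormal eyes supplies numerators only, and the reader must count them. It does not say how many eyes were examined, so it gives no rate for either technique. A reader of the study report could not see directly whether corneal, anterior-segment or retinal findings were more frequent after CRS or after manual surgery.

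The adverse event tables fill part of this gap. Under protocol 13.2, an untoward change in a protocol-specific parameter becomes an adverse event only if the investigator considers it clinically relevant. Abnormal findings below that threshold would appear in a listing and in no table.

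There is also a question of plan integrity. SAP section 1 says the SAP sets out any planned deviations from the protocol, yet 6.3.4 and 6.3.6 do not present listing-only output as one.

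**Working it through.** The plan gives no figure to reproduce on this point. The check matches each safety endpoint to its planned output.

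**Step 1. Planned output for the six endpoints**

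| Safety endpoint | SAP section | By-group table planned? | Listing planned? |
|---|---|---|---|
| Adverse events | 6.3.2 | Yes: eye counts, event counts, percentages | Yes |
| Device deficiencies | 6.3.3 | Yes: number | Yes |
| Slit-lamp examination | 6.3.4 | No | Yes |
| IOP | 6.3.5 | Yes: descriptive statistics by visit | Yes |
| Dilated fundus examination | 6.3.6 | No | Yes |
| Surgical problems | 6.3.7 | Yes: numbers and percentages | Yes |

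Four of six have a by-group table, and 6 − 4 = 2 do not. IOP and surgical problems each get a table and a listing, described separately. The SAP therefore treats these as different outputs, and the listings in 6.3.4 and 6.3.6 cannot be read as including a table.

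**Step 2. Who promised what**

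- Slit lamp: promised in protocol 15.7, in the synopsis for safety outcomes in general, and in SAP 4.3. The SAP conflicts with the protocol and with itself.
- Fundus: promised in protocol 15.7 and, in general terms, in the synopsis. The visible text of SAP 4.3 does not name it, so the conflict is between protocol and SAP only.

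**Step 3. Does the version gap explain it?** The SAP states that it is based on protocol Version 1.0, and the protocol supplied is Version 3.0. The visible entries for Amendments 1 and 2 show no change to slit-lamp or fundus reporting, so they do not account for the mismatch.

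**Step 4. How much data is involved.** Protocol Table 6-1 schedules slit lamp after surgery at Visits 1, 1A, 2A, 3A and 4A, and fundus after surgery at Visit 4A. Protocol 9.3 assigns Visit 1 to the first eye, Visit 2A to the second eye, and Visits 1A, 3A and 4A to both.

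- First eye: Visits 1, 1A, 3A, 4A = 4 slit-lamp examinations.
- Second eye: Visits 1A, 2A, 3A, 4A = 4 slit-lamp examinations.
- Per subject: 4 + 4 = 8 slit-lamp and 2 fundus examinations.
- For 300 to 500 treated subjects with full attendance: 300 × 8 = 2,400 to 500 × 8 = 4,000 slit-lamp examinations, and 300 × 2 = 600 to 500 × 2 = 1,000 fundus examinations.

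**Step 5. Postoperative time behind each visit label.** The second eye is operated on 7 to 14 days after the first.

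| Visit | First eye | Second eye |
|---|---|---|
| 1 | Day 1 | not applicable |
| 1A | Days 8–15 | Day 1 |
| 2A | not assigned | Days 7–10 |
| 3A | Days 20 + 7 = 27 to 40 + 14 = 54 | Days 20–40 |
| 4A | Days 70 + 7 = 77 to 110 + 14 = 124 | Days 70–110 |

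The upper limit of 124 days agrees with protocol 9.1. Visit 1A combines eyes at Day 1 with eyes at Days 8–15, so a table by visit label alone would mix postoperative times there.

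**The case against.** The strongest reply is that little is lost. Both listings carry procedure group, so abnormal eyes can be identified by technique. Clinically relevant changes must be reported as adverse events regardless of causality, and ocular adverse events are tabulated by procedure group. SAP 6.2 sets no formal safety hypotheses. SAP section 2 has a general convention that categorical variables are presented with frequency and percentage, which suggests that percentages were not dropped on purpose. The study is post-market, the devices are commercially available, and tables can be added before database lock.

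Much of this stands. A reader might infer that the two examinations are never compared between techniques. The documents do not support that, because of the procedure-group column and the adverse event tables. What is missing is a descriptive summary of the findings as such.

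A reader might also infer that protocol 15.7 requires tables by arm, by visit and by worsening from baseline. It does not. It specifies presentation by treatment for ocular adverse events and device deficiencies, but for these examinations only a summary with number and percentage.

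The reply does not remove the mismatch. The convention in SAP section 2 names neither examination and creates no table where 6.3.4 and 6.3.6 specify a listing. The adverse event route leaves out findings judged not clinically relevant. The synopsis promises summaries in addition to listings.

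**Conclusion.** The point holds in a limited form. The SAP's listing-only output for slit lamp and fundus does not meet the commitment in protocol 15.7 and the synopsis. For slit lamp it also conflicts with SAP 4.3. The departure is not declared. Two of six safety endpoints are left without a number, percentage or denominator by procedure group.

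Two further inferences should be avoided. The first is that the SAP contradicts itself on both examinations; the visible text shows this for slit lamp only. The second is that slit lamp yields paired data at five visits. Visits 1 and 2A cover one eye each, and at Visit 1A the two eyes are at different postoperative times. Only Visits 3A and 4A offer pairs at broadly similar times.

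The conclusion rests on the visible text, on the assumption that no redacted passage holds the missing summaries, and, for the examination counts, on full attendance. No primary or secondary effectiveness result is affected. It is worth correcting because a stated commitment is unmet and the remedy is small.

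**What to change.** In SAP 6.3.4 and 6.3.6, add tables of the number and percentage of eyes in the safety analysis set with each abnormal finding, by procedure group, with the number of eyes examined as the denominator. Keep the listings. Protocol 15.7 requires the number and percentage; the by-group layout follows the SAP's other safety tables.

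Present slit lamp by each eye's postoperative time: Day 1 (Visit 1 for the first eye, Visit 1A for the second), about Week 1 (Visit 1A for the first eye, Visit 2A for the second), Month 1 (Visit 3A) and Month 3 (Visit 4A). Present fundus at Visit 4A. A count of eyes that worsened from baseline would be a useful option, but 15.7 does not commit to it.

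If listing-only output is intended, the SAP should instead declare and justify it as a deviation from protocol 15.7, and correct the slit-lamp reference in SAP 4.3.

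The cost is two descriptive tables from data already collected, with no added visits or assessments and no effect on sample size or type I error.

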### **6.3.5 Intraocular Pressure**

IOP measurements will be recorded in mmHg and rounded to the nearest whole mmHg.

Descriptive summaries for continuous variables of observed IOP values and change from baseline values will be presented by procedure group and visit.

A listing will be provided which presents all subjects with an increase or decrease in IOP of more than 10 mmHg at any visit compared to the same eye at baseline. The listing will include the following variables: procedure group, investigator, subject, age, sex, race, ethnicity, visit, eye, baseline value, value at the visit, and change from baseline value.

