6 SCHEDULE OF VISITS

Table 6-1 Schedule of Visits

Procedure/Assessment	Nominal Time ± Visit Window Limits								
	Visit 0 Both eyes assessed	Visit 00	Visit 1	Visit 00A	Visit 1A Both eyes assessed	Visit 2A	Visit 3A Both eyes assessed	Visit 4A Both eyes assessed	USV ⁿ
Procedure/Assessment	Day -30 to -1 Screening for both eyes	Day 0 Implant for Eye 1	Day 1 for Eye 1	Day 7-14 Implant for Eye 2 (7-14 days after V00)	Day 1 for Eye 2; Days 8-15 for Eye 1	Day 7-10 post 2 nd eye surgery	Month 1 (Days 20-40 post 2 nd eye surgery)	Month 3 (Days 70-110 post 2 nd eye surgery)	N/A
Informed consent ^a	X								
Demographics	X								
Medical history	X								
Concomitant medications	X	X	X	X	X	X	X	X	X
Inclusion/exclusion criteria	X								
Pregnancy test ^b	X								
Randomization ^c	X								
IOP ^d	X		X		X			X	X
Corneal topography	X								
Manifest refraction	X				X	X	X	X	X
Predicted post-op spherical equivalent (SE)	X								
Slit-lamp examination	X		X		X	X	X	X	X

Procedure/Assessment	Nominal Time ± Visit Window Limits									Status: Effective
	Visit 0 Both eyes assessed	Visit 00	Visit 1	Visit 00A	Visit 1A Both eyes assessed	Visit 2A	Visit 3A Both eyes assessed	Visit 4A Both eyes assessed	USV ⁿ	
Day -30 to -1 Screening for both eyes	Day 0 Implant for Eye 1	Day 1 for Eye 1	Day 7-14 Implant for Eye 2 (7-14 days after V00)	Day 1 for Eye 2; Days 8-15 for Eye 1	Day 7-10 post 2 nd eye surgery	Month 1 (Days 20-40 post 2 nd eye surgery)	Month 3 (Days 70- 110 post 2 nd eye surgery)	N/A		
Tear Break Up Time (TBUT)	X ^o									
Dilated fundus examination	X							X		
Biometry (LenStar)	X									
Keratometric measurements	X							X	X	
Use Verion Vision Planner for IOL power calculation) ^f	X									
Verion (digital marker L, digital marker M) ^g		X		X						
LenSx arcuate incisions ^h		X		X						
CDE		X		X						
Estimated aspiration fluid		X		X						
Phaco aspiration time		X		X						
VerifyEye+ measurement with or without VerifyEye Lynk ^{g, i}		X		X						
Problems during surgery ^j		X		X						
Manual LRI ^k		X		X						
Device deficiencies	X	X	X	X	X	X	X	X	X	

Procedure/Assessment	Nominal Time ± Visit Window Limits									
	Visit 0 Both eyes assessed	Visit 00	Visit 1	Visit 00A	Visit 1A Both eyes assessed	Visit 2A	Visit 3A Both eyes assessed	Visit 4A Both eyes assessed	USV ⁿ	

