7.2 Clinical Study Design

This is a prospective, multi-center, observer-masked, randomized, active control (standard manual technique), contralateral design study to evaluate refractive predictability between CRS and standard manual technique. All products under investigation are commercially available in the countries where the study is being conducted.

The eye with the worse preoperative best-corrected distance visual acuity (BCDVA) will undergo cataract surgery with IOL implantation first. If the preoperative BCDVA is equal in both eyes, then the right eye will undergo the surgery and IOL implantation first. The first eye will be randomized to receive the test or control treatment; the fellow eye will receive the opposite assignment. Subjects are required to attend 8 study visits, during which assessments will be scheduled separately for the first study eye, the second study eye and both study eyes.

[figure not shown]
Subjects will attend the Screening visit from Day -30 to Day -1 (Surgery Eye 1, Visit 00), followed by Visit 1 (Day 1 post surgery for Eye 1), Visit 00A (Surgery Eye 2 [7-14 days after that for Eye 1]), Visit 1A for both eyes (Day 1 for Eye 2; Day 8-15 for Eye 1), Visit 2A (Day 7-10 post Eye 2 surgery), Visit 3A (Month 1 [Day 20-40 post Eye 2 surgery]), Visit 4A (Month 3 [Day 70-110 post Eye 2 surgery]). Total expected clinical study duration will be approximately 5 months after being screened for study eligibility.

This study will employ an adaptive design with a potential sample size adjustment based on interim analysis (Section 15.8). It is planned that the study will enroll approximately 350 subjects to initially randomize and treat 300 subjects (that could potentially increase to approximately 580 subjects enrolled and 500 subjects randomized). An interim analysis will be performed once 200 subjects have been randomized, treated and completed 1-month follow-up visits. An additional 200 subjects may be randomized and treated beyond the initially planned 300 subjects. Thus the study will randomize and treat between 300 and 500 subjects.

An overview of the study design is presented in **Figure 7-1**.

Figure 7-1

Study Design

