VerifEye+: The following conditions may affect the accuracy of measurements taken by VerifEye+. Progressive retinal pathology such as diabetic retinopathy, macular degeneration, or any other pathology that the physician deems would interfere with patient fixation.

Corneal pathology such as Fuchs', epithelial basement membrane dystrophy (EBMD), keratoconus, advanced ptelygium impairing the cornea, or any other pathology that the physician deems would interfere with the measurement process. Residual viscous substances left on the corneal surface such as lidocaine gel or viscoelastics. Visually significant media opacity, such as prominent floaters or asteroid hyalosis. Retro or peribulbar block, or any other treatment that impairs a patient's ability to visualize the fixation light. Utilization of iris hooks during surgery. Pupil dilation less than 4.5 mm.

Standard manual technique: The following complications may occur with the standard manual technique.

- Incomplete or intenupted capsulotomy
- Capsular tear
- Corneal abrasion or defect
- Infection
- Damage to intraocular strnctures
- Anterior chamber fluid leakage
- Anterior chamber collapse

Another risk associated with phacoemulsification is rise in IOP. The response in IOP to phacoemulsification is biphasic, with a transient immediate rise followed by a modest long-te1mdecrease. Postoperative IOP usually peaks 5- 7 h after surgery and returns to normal levels in 1-3 days. Although transient, the elevated IOP can cause ocular pain, may increase the risk of sight threatening complications such as retinal vascular occlusion, progressive field loss in advanced glaucoma, and anterior ischemic optic neuropathy in susceptible patients (Karatas 2013).

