12.1.4 Post-Surgery Visit (Visit 1A, 2A, 3A and Visit 4A)

Below is a list of study procedures to be undertaken at post-surgery visits. Procedures should be performed in the order presented below. All assessments must be recorded in source documents and eCRFs (if applicable).

Ocular assessments are to be performed in the study eye only.

1. Document changes in ocular and nonocular concomitant medications at Visit 1A, 2A, 3A, and Visit 4A.
2. [REDACTED]
3. [REDACTED]
4. [REDACTED]
5. [REDACTED]
6. Perform manifest refraction assessment at Visit 1A, 2A, 3A, and Visit 4A. However, at Visit 1A, assessments will be performed at the Week 1 visit for eye 1 only (Refer to MOP for details).
7. [REDACTED]
8. Perform slit-lamp examination at Visit 1A, 2A, 3A, and Visit 4A. Refer to MOP for details.
9. [REDACTED]
10. [REDACTED]
11. Perform Keratometric measurements at Visit 3A and Visit 4A.
12. Perform IOP at Visit 1A and 4A only. IOP should be measured after all VAs, corneal

measurements and refractive findings have been obtained. Refer to MOP for details.

13. Perform dilated fundus exam at Visit 4A only. Refer to MOP for details.

14. Record any device deficiencies and AEs. Refer to Section 13 for further detail.

15. Document subject exit from study at Visit 4A.

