### 5.3.1 Primary Effectiveness endpoint

[figure not shown]
The primary effectiveness analysis will be analyzed using a one-sided McNemar's test at the 5% significance level. P-value for the difference in the population proportions will be estimated and presented.

[figure not shown]
The number and percentage of eyes with manifest refraction spherical equivalent  $\leq 0.5D$  of predicted post-operative spherical equivalent will be presented by surgery procedure and visit.

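### SAP 6.3.5 tabulates IOP by visit, but Visit 1A is Day 1 for second eyes and Days 8-15 for first eyes, so that one row mixes two postoperative times

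*SAP*

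**What the plan says.** For IOP, SAP 6.3.5 states: "Descriptive summaries for continuous variables of observed IOP values and change from baseline values will be presented by procedure group and visit". The same section adds a listing of every eye whose IOP moves more than 10 mmHg from its own baseline.

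Visits are numbered per subject. The second surgery follows the first by 7 to 14 days (Protocol 7.2). Table 6-1 marks Visit 1A as a visit at which both eyes are assessed, and times it as "Day 1 for Eye 2; Days 8-15 for Eye 1".

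Table 6-1 places IOP at Visits 0, 1, 1A and 4A and at unscheduled visits. Protocol 12.1.3 has it at Visit 1, which is Day 1 for the first eye. For the later visits Protocol 12.1.4 says "Perform IOP at Visit 1A and 4A only", with no restriction to one eye.

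The technique for the first eye is randomised and the fellow eye gets the other one (Protocol 7.2). SAP 2.2 dates baseline from each eye's own surgery. No visible SAP text applies a similar rule to post-surgery visits.

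**The concern.** Each procedure column contains both first and second eyes. At Visit 1A these are at different postoperative times, and the by-visit rule averages them. The protocol itself separates the two times: Section 9.4.1 says that IOP rises after phacoemulsification and "returns to normal levels in 1-3 days". On that account an eye at Day 1 may still be raised, while an eye at Days 8-15 should not be.

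IOP is a named safety endpoint. Protocol 9.4.1 lists raised pressure among the possible complications of the laser, and names IOP rise as a risk of phacoemulsification, which both eyes undergo. An early IOP comparison is therefore a natural thing for a reader of the report to look for. Under the rule as written, the Visit 1A row describes no single postoperative time. Within every subject, the two eyes in that row are not at the same stage.

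**Working it through.** **1. Reproduce the stated window.** Second surgery is 7 to 14 days after the first, and Visit 1A is one day later. First eye at Visit 1A: 7 + 1 = Day 8 to 14 + 1 = Day 15. This agrees with Table 6-1.

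**2. Which eyes have IOP, and when** (Table 6-1, Protocol 12.1.3 and 12.1.4):

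| Visit | First eye | Second eye |
|---|---|---|
| 1 | Day 1 | not yet operated |
| 1A | Days 8-15 | Day 1 |
| 4A | Days 77-124 | Days 70-110 |

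For Visit 4A, the first-eye range is 70 + 7 to 110 + 14. The offset there is small relative to the elapsed time. Only Visit 1A combines clearly different states.

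**3. Counts in the Visit 1A row.** Let q be the share of subjects whose first eye is CRS. The documents do not state the ratio, so q = 0.5 is assumed and 0.45 to 0.55 is shown. Complete data are assumed.

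- 300 subjects, q = 0.5: each column holds 150 Day 1 eyes and 150 Days 8-15 eyes.
- 500 subjects, q = 0.5: 250 and 250.
- 300 subjects, q = 0.45: CRS column 165 Day 1 and 135 Days 8-15; manual column 135 and 165. At q = 0.55 these are reversed.

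**4. Effect on the means.** Let r be the mean Day 1 rise common to both procedures and d an extra Day 1 rise with CRS. Assume that both are gone by Days 8-15. In the CRS column the Day 1 eyes are the second eyes, a share of 1 − q; in the manual column the share is q.

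- CRS column mean = (1 − q)(r + d)
- Manual column mean = q × r
- Difference = (1 − 2q) r + (1 − q) d

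At q = 0.5 the difference is 0.5d, and a common rise r appears as 0.5r.

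**5. Illustration.** The documents give no IOP means or SDs, so r = 3 mmHg and d = 2 mmHg are assumed.

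| q | CRS column | Manual column | Difference shown | Day 1 truth |
|---|---|---|---|---|
| 0.45 | 0.55 × 5 = 2.75 | 0.45 × 3 = 1.35 | 1.4 | 2.0 |
| 0.50 | 0.50 × 5 = 2.50 | 0.50 × 3 = 1.50 | 1.0 | 2.0 |
| 0.55 | 0.45 × 5 = 2.25 | 0.55 × 3 = 1.65 | 0.6 | 2.0 |

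With no true difference (d = 0) and r = 3, the row shows (1 − 2q) × 3: +0.3 at q = 0.45, 0 at q = 0.5 and −0.3 at q = 0.55. Bias therefore arises only if the order is unbalanced, and is small over this range.

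**6. After re-mapping by time since surgery.** Day 1 pools Visit 1 (first eyes) with the second eyes at Visit 1A. At 300 subjects with q = 0.5 that is 150 + 150 = 300 Day 1 eyes per procedure, and the difference shown is d. Days 8-15 becomes its own row of about 150 eyes per procedure, all first eyes.

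**The case against.** Several points on the other side stand.

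- **A clean Day 1 row exists.** Visit 1 is Day 1 for first eyes, and the technique for first eyes is randomised. At 300 subjects it gives about 150 CRS against 150 manual eyes, unmixed. A reader might infer that the plan has no valid Day 1 IOP comparison. It has one, limited to first eyes.
- **Dilution is not bias.** A reader might infer that the Visit 1A comparison is biased. With balanced order both columns carry the same mix, so it is not.
- **Individual spikes are not hidden.** The SAP 6.3.5 listing gives eye, visit and procedure for every change above 10 mmHg, and clinically relevant changes are reportable as adverse events (Protocol 13.2). Only a shift in means below that threshold is blurred.
- **No test depends on it.** SAP 6.2 sets no safety hypotheses. Pooling all Day 1 eyes might suggest a gain in precision from pairing, but the SAP plans no paired IOP contrast, so no such gain is claimed here.
- **The Day 1 state is itself uncertain.** The protocol puts the usual peak a few hours after surgery, and some eyes may be back to normal by Day 1. Then r and d are small and little is lost.

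A reader might also extend the point to SAP 5.3.1, where the share of eyes within 0.5 D "of predicted post-operative spherical equivalent will be presented by surgery procedure and visit". The documents do not support that. For refraction, Protocol 12.1.4 says that "at Visit 1A, assessments will be performed at the Week 1 visit for eye 1 only", and Protocol 9.3 assigns Visit 2A to the second eye. Each of those rows is homogeneous in postoperative time.

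Two textual doubts remain. SAP 2.1 is a heading with no visible text, so a visit definition may have been removed. A Table 6-1 footnote restricting some assessments to the first eye has lost its marker; the visible text ties similar wording to refraction, not to IOP.

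**Conclusion.** The concern holds for one row of one descriptive safety table. As SAP 6.3.5 reads, the Visit 1A row averages Day 1 and Days 8-15 eyes within each procedure. A Day 1 rise or procedure difference that has resolved by Days 8-15 appears there at about half size. No summary described in the SAP shows Day 1 IOP for all CRS eyes against all manual eyes.

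The halving rests on 1:1 order and on full resolution by Days 8-15. The first is assumed; the second follows the protocol's own account of IOP recovery. The mmHg figures are illustrations only. The mixing itself rests on the visible text: both eyes have IOP at Visit 1A and no per-eye visit mapping is given.

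The primary Month 1 analysis is unaffected. The point is worth acting on because the correction is almost free, not because a conclusion of the trial depends on it.

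**What to change.** In SAP 6.3.5 only, tabulate early IOP by time since each eye's own surgery, extending the per-eye principle of SAP 2.2:

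- **Day 1:** Visit 1 for the first eye plus Visit 1A for the second eye.
- **Days 8-15:** Visit 1A for the first eye, as a separate row labelled first eyes only.
- **Month 3:** Visit 4A, unchanged.

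The Day 1 row relies on the Visit 1 measurement. Table 6-1 and Protocol 12.1.3 include it, but the post-surgery IOP list in Protocol 9.3 names only Visits 1A and 4A. Those passages should be reconciled.

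The cost is a few lines of SAP text and one visit-mapping step in the programs. No new data are needed, and SAP 5.3.1 needs no change on this account.
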